**Table 3. Systolic, diastolic, and mean blood pressures at time of initiation of therapy. Mean (SD).**

	First fluid bolus		First vasopressor dose		First steroid dose	
	<37 wks GA N = 168	≥37 wks GA N = 324	<37 wks GA N = 66	≥37 wks GA N = 149	<37 wks GA N = 30	≥37 wks GA N = 73
Systolic BP	53.3 (10.7)	58.8 (14.3)	47.9 (8.5)	52.7 (12.5)	49.2 (13.1)	55.2 (13.0)
Diastolic BP	30.5 (13.0)	43.2 (10.9)	29.5 (15.1)	31.4 (10.3)	32.2 (10.8)	36.1 (9.4)
Mean BP	38.4 (9.8)	42.4 (11.8)	35.6 (7.7)	39.1 (10.1)	39.1 (11.2)	43.4 (10.3)

**Table 4. Therapy received for cardiovascular insufficiency; timing, blood pressure at time of initiation and total days of therapy. Median (25th percentile, 75th percentile); % (n/N)**

	All N = 502	Volume expanders N = 488	Inotropes N = 215	Steroids N = 103
Age at 1 st dose (hours)	4.0 (1.2, 15.1)	3.5 (1.1, 14.8)	12.633 (5.03, 24.7)	26.2 (12.4, 43.5)
Mean BP at 1 st dose	39 (33, 47)	39 (33, 47)	36 (31, 42)	41 (35, 49)
% with mean BP <PMA	39.2% (131/334)	39.8% (137/344)	53.8% (93/173)	32.6% (30/92)
Total Days	NA	NA	2.5 (1, 5)	4 (2, 7)

The timing of therapy is outlined above in Table 4. Most infants had therapy initiated for cardiovascular insufficiency within the first 24 hours of age.

Low blood pressure was not the only clinical measure used to initiate therapy for cardiovascular insufficiency and appears to be an unreliable measure. Therefore, the presence of inotropes was used to evaluate outcomes. The patient characteristics and outcomes are listed in Tables 5 and 6. Outcomes were significantly worse in those who received inotropes vs. those who did not.

**Table 5. Patient characteristics of infants who received inotropes vs. those who did not**

Patient Characteristic	All Infants N=783	Inotrope N=212	No inotropes N=571	P-value
Prenatal steroid use, %	6.0 (47/778)	4.8 (10/210)	6.5 (37/568)	0.4586
Birth weight, g	3001 (646)	3145 (671)	2948 (629)	0.0001
Gestational age, wks	37.3 (2.1)	37.8 (2.1)	37.1 (2.1)	<.0001
Apgar score <3 at 5 min, %	12.1 (93/771)	18.8 (39/208)	9.6 (54/563)	0.0008
Intubation in L & D, %	39.8 (311/782)	54.7 (116/212)	34.2 (195/570)	<.0001
Cesarean section, %	55.8 (437/783)	56.1 (119/212)	55.7 (318/571)	1.0000
Male, %	60.7 (475/782)	62.7 (133/212)	60.0 (342/570)	0.5392
Outborn, %	43.6 (341/782)	30.7 (65/212)	48.4 (276/570)	<.0001
Inhaled NO, %	19.3 (151/781)	54.7 (116/212)	6.2 (35/569)	<.0001
Extra corporeal membrane oxygenation (ECMO), %	4.7 (37/781)	14.2 (30/212)	1.2 (7/569)	<.0001
Surfactant use, %	42.1 (329/781)	52.4 (111/212)	38.3 (218/569)	0.0006
Whole body cooling, %	10.8 (84/781)	22.2 (47/212)	6.5 (37/569)	<.0001

**Table 6-1. Outcomes in infants who received inotropes vs. those who did not**

Outcome	All Infants N=783	Inotropes N=212	No inotropes N=571	P-value
Death, %	6.8 (53/778)	15.7 (33/210)	3.5 (20/568)	<.0001
Died within 7 days, %	3.0 (23/778)	8.6 (18/210)	0.9 (5/568)	<.0001
Age at time of death	9.0 (3.0, 26.0)	7.0 (3.0, 11.0)	25.5 (8.0, 52.5)	0.0054
Days intubated and on vent	3.0 (2.0, 8.0)	8.0 (4.0, 13.0)	2.0 (2.0, 5.0)	<.0001
Days on oxygen	6.0 (2.0, 11.0)	10.0 (6.0, 17.0)	4.0 (2.0, 8.0)	<.0001
Day of life at time of full nipple feeding	9.0 (6.0, 17.0)	16.0 (10.0, 26.0)	8.0 (5.0, 14.0)	<.0001
Days in NICU	12.0 (8.0, 24.0)	16.0 (10.0, 34.0)	11.0 (8.0, 21.0)	<.0001

**Table 6-2. Outcomes in infants by gestational age who received inotropes vs. those who did not; excluding infants with CDH, HIE, receipt of whole body cooling, and omphalocele,**

Outcome	All Infants	Inotropes	No Hypotension by any definition	* signified p-value is <0.5 between groups
GA < 37 weeks	N = 277	N = 42	N = 115	
Death (%)	3.2	14.3	0 (0/115)	*
Died within 7 days (%)	1.4	9.5	0 (0/115)	*
Age at time of death 	9 (4, 16)	4 (3, 16)	NA	NA
Days intubated and on ventilator	2 (2, 5)	7 (4, 11)	2 (2, 4)	*
Days on oxygen	5 (2, 9)	10.5 (4, 16)	4 (2, 8)	*
DOL at time of full nipple feeding	9 (6, 17)	20.5 (10, 27)	8 (6, 14)	*
Days in NICU	12 (8, 24.5)	16 (10, 34)	10 (6, 17)	*

GA ≥ 37 weeks	N = 370	N = 93	N = 113	
Death (%)	4.3	9.8	2.7	*
Died within 7 days (%)	1.4	4.4	0.0	*
Age at time of death	12.5 (2, 45.5)	12 (2, 18)	48 (30, 60)	
Days intubated and on ventilator	3 (2, 8)	9.5 (4, 13)	2 (1, 4)	*
Days on oxygen	5 (2, 10)	11 (8, 18.5)	3 (1, 5)	*
DoL at time of full nipple feeding	8 (5, 15)	14 (10, 26)	6 (3, 9)	*
Days in NICU	12 (7, 21)	17 (11, 35)	8 (5, 15)	*

## 7. Methods/Procedures

### a. Study Design

The study will be a randomized, multicenter, double-blind, placebo-controlled trial. Patients will be enrolled and randomized in a variable block design, 1:1 ratio of hydrocortisone or placebo.

### b. Study Population

**Inclusion criteria:** Eligible infants will be ≥34 weeks gestation who are—

- Intubated and mechanically ventilated for a minimum of 2 hours before 72 hours postnatal age
- Admitted to a NRN NICU before 48 hours postnatal age.

Information will be collected on maternal and infant demographics including antenatal steroids. Data will also be collected on eligible infants who are not enrolled on the screening and eligibility form including gestational age, outborn/inborn status, and reason for not enrolling.

The exclusion criteria include those infants with cardiovascular insufficiency which is likely not due to relative adrenal insufficiency.

**Exclusion criteria:**

- Attending physician refusal
- No parent/guardian consent
- Infants receiving extracorporeal membrane oxygenation (ECMO)
- Infants who are intubated for the sole purpose of an anticipated surgery or airway anomalies
- Infants for whom treatment will be limited based on poor prognosis
- Receiving dexamethasone or hydrocortisone
- Receiving ibuprofen or indomethacin

Infants will be excluded if there is a known diagnosis at the time enrollment of—

- Congenital heart disease not including atrial septum defect, ventricular septal defect or patent ductus arteriosus
- Hypotension thought to result from specific, immediately remediable factors including placental hemorrhage, acute hemorrhage, or tension pneumothorax
- Pituitary hypoplasia or congenital adrenal hyperplasia
- Chromosomal disorder
- Hypertension in the absence of inotrope therapy as defined by a mean arterial blood pressure >95th percentile for postmenstrual age in weeks
- Receipt of therapeutic hypothermia for hypoxic ischemic encephalopathy
- Severe brain structural abnormalities or periventricular leukomalacia, stroke or seizures
- Congenital diaphragmatic hernia

- Abdominal wall defects, such as gastroschisis or omphalocele
- Major renal anomalies requiring dialysis.

Infants diagnosed with pituitary hypoplasia or congenital adrenal hyperplasia will be discontinued from study drug and withdrawn from study. All other infants in whom study drug is discontinued, including those treated with ECMO after enrollment will remain in the analysis according to the intention –to- treat principle.

**Timing of consent.** Parents/guardians of infants who meet inclusion criteria and who do not have any of the exclusion criteria may be approached for consent for enrollment into the study, regardless of any blood pressure values or therapies planned or given for cardiovascular insufficiency. Infants ideally would be enrolled and randomized to study drug within 24 hours of intubation and receipt of inotropes (up to max of 96 hours of age). For transported infants, parents will be contacted for consent by telephone. Enrolling infants as soon as possible will allow more time for discussion with parents, enrollment, randomization, and receipt of study drug.

### c. Study Intervention

**Randomization criterion. Decision of the clinical care team to treat with** an inotrope (dopamine, dobutamine, epinephrine, or norepinephrine) within the first 72 hours of life, at a minimum dose of 5 mcg/kg/min (epinephrine 0.01 mcg/kg/min), will be the trigger for randomization to study drug. Blood pressure will **not** be a criterion for randomization. Low dose dopamine (<5mcg/kg/min) initiated for low urine output does not qualify for randomization. Low blood pressure did not correlate with interventions for cardiovascular insufficiency in our multicenter NRN observational study (see section 6b, *Preliminary Studies, above*). However, receipt of inotrope support was associated with significantly worse outcomes, including a mortality rate of almost 16% vs. 4%. Therefore, this is a reasonable clinical indicator of adverse outcomes.

**Randomization method.** Randomization will be stratified by Network center using a randomly permuted block randomization algorithm devised by the NRN Data Coordinating Center at RTI. A centralized secure, password-protected web-based (Hatteras Clinical DMS) randomization process will be used to allocate infants to either hydrocortisone or placebo. The medication will be reconstituted by the pharmacist, and caregivers will remain blinded. Placebo will be normal saline and will be given in equal volume to a hydrocortisone dose and delivered at same rate.

**Study Drug.** Enrolled infants who receive inotrope therapy before 72 hours postnatal age **will be randomized to receive 7 days of hydrocortisone** (hydrocortisone sodium succinate, plain; will not have benzyl alcohol) given through intravenous line, po if no line or by intramuscular injection (I.M.) (if no intravenous line and infant is NPO) **or 7 days of intravenous, po or I.M. placebo** (normal saline in equal volume). Hydrocortisone dosing will be 2.5 mg/kg/day on day 1, 2 mg/kg/day on days 2 and 3, 1 mg/kg/day on days 4 and 5, then 0.5 mg/kg/day on days 6 and 7.

- 1 mg/kg loading dose x 1
- 0.5 mg/kg q 6 hours x 12 doses
- 0.5 mg/kg q 12 hours x 4 doses
- 0.5 mg/kg q day x 1 dose

We will continue hydrocortisone for 7 days, weaning after the first 3 days, to avoid possible rebound hypotension and in consideration of possible down-regulation of glucocorticoid

receptors by higher cortisol concentrations. Therapy with active drug or placebo should be instituted ideally within 12-24 hours of initiation of inotrope therapy. All other treatments will be at the discretion of the clinical care team. This real-world management design will increase generalizability of study results and improve compliance with study procedures.

*Rationale for hydrocortisone dosing: see section 6, Background, for rationale on dosing.*

**Laboratory.** One blood sample (1ml) for a cortisol level will be obtained within 4 hours prior to initiation of study drug for each enrolled patient. The sample of blood from each center will be labeled study patient ID and shipped to a central laboratory (The University of New Mexico CTSC Research Lab) in Albuquerque, New Mexico. The cortisol levels will be measured by the IMMULITE 1000 cortisol procedure (chemiluminescent system).

Blood for cortisol levels is not mandatory for study if parents wish to decline blood draw for this timed study lab. Cortisol levels obtained by clinical team will be collected from medical chart. The relationship between cortisol concentrations and response to hydrocortisone, severity of illness and outcomes will be analyzed.

The literature shows conflicting results on the value of cortisol concentrations in determining therapy. Infants often respond to glucocorticoids regardless of cortisol levels. While we found that infants with cortisol values <15 mcg/dl had positive responses to hydrocortisone in a small retrospective study, other studies were unable to use cortisol values to predict the severity of illness, need for cardiovascular support, or the response to treatment.

**Echocardiograms.** If an echocardiogram is ordered by the clinical team, the clinical report will be labeled with patient ID and will be sent to the NRN Data Coordinating Center at RTI. The following measurements will be collected if available: shortening fraction, ejection fraction presence of ductus and diameter, Left atrium to aortic ratio, presence of diastolic retrograde flow in descending aorta, velocity in left pulmonary artery, pressure gradient across PDA and shunt direction, tricuspid regurgitation, right ventricular function, evidence of pulmonary hypertension, atrial and ventricular dimensions, isovolumic relaxation and contraction times, presence of any defects and myocardial performance indices if available (some institutions do not have equipment to determine indices like wall stress).

**Concurrent medications.** All concurrent medications just prior and during the course of study drug administration will be recorded including dopamine, dobutamine, epinephrine, norepinephrine, milrinone, vasopressin, sedatives (i.e. morphine, fentanyl, versed), any steroids, respiratory medications (i.e. inhaled nitric oxide, surfactant), neuromuscular blockers and prostaglandins. Inotrope duration and dosing (maximum drip doses) will be specifically collected for evaluation of study drug effect in addition to collecting total fluid volume received. Inotropes and volume expanders may be given as directed by clinical team. Once patients are enrolled in the study, they will not be allowed to receive dexamethasone or indomethacin/ibuprofen while on study drug. Dexamethasone is an extremely potent glucocorticoid, and risks of using the two steroids at the same time are unknown. The concurrent use of dexamethasone for airway edema will not be allowed. The combined use of a glucocorticoid and indomethacin is associated with spontaneous intestinal perforation in very preterm newborns. Although our study population should not be at risk of this complication, it seems prudent to avoid this combination therapy. Initiation of indomethacin or ibuprofen or any anti-hypertensive medication will result in

discontinuation of study drug. Data collection will continue and all analysis will be intention to treat.

**Open-label hydrocortisone will be discouraged.** If the attending physician feels that it is necessary to administer open-label hydrocortisone for vasopressor (inotrope)-resistant hypotension, we will first encourage maximum vasopressor (inotrope) therapy, to include at least a dopamine dose of 10 mcg/kg/min and a second drug at a dose of at least 10 mcg/kg/min of dobutamine or 0.1 mcg/kg/min of epinephrine. We will recommend dosing of hydrocortisone as outlined in this protocol. The max total daily dose that any infant would receive if open-label hydrocortisone were used would be 5 mg/kg/day. Some small studies have used up to 5-7 mg/kg/day without adverse events. Some providers obtain cortisol values to direct therapy but cortisol values obtained in this population have shown very little correlation to severity of illness or response to therapy we recommend, until more data is available, that cortisol values are not used to direct therapy. Data collection will continue, and all analyses will be intention to treat.

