### **Other Potential issues**

- **Adrenal suppression.** Even in the most premature infants, this brief period of therapy has not previously been associated with adrenal suppression. If any infant shows signs consistent with adrenal insufficiency after discontinuation of the study drug (hypotension, oliguria, hyponatremia, hyperkalemia), a blood sample can be sent for cortisol and therapy with hydrocortisone reinstated if deemed necessary by the clinical care team.
- **Neurodevelopmental deficits.** The neurodevelopmental benefits or risks of using hydrocortisone for the treatment of cardiovascular insufficiency is unknown. This RCT will be an important addition to the literature regarding long-term risks/benefits of this therapy. No previous study has shown adverse neurodevelopmental effects of hydrocortisone treatment in the newborn period in extremely low birth weight infants. Because this study population is more mature, it is even less likely to adversely impact this proposed study population; however, our study design will enable us to evaluate that issue.
- **Persistent hypotension.** Infants will be treated in the routine manner by the attending clinicians in their respective centers to allow real-world design. Open-label hydrocortisone is discouraged but if given, the recommended plan is listed in the methods section above. Data on infants who receive open-label hydrocortisone will be collected and/or on infants who receive 3 different types of inotropes or more.

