### **Data Safety and Monitoring Committee (DSMC) Safety Monitoring.**

#### a. Adverse events to be monitored

Adverse events to be monitored will be those previously associated with glucocorticoid therapy, including hyperglycemia, hypertension and gastrointestinal perforation. Any infant who develops new, sustained hyperglycemia (>180mg/dl on at least two determinations at least 6 hours apart or receiving insulin) or new, sustained hypertension (mean arterial pressure >95th percentile for age on four serial determinations over at least 12 hours or receiving antihypertensive) may have study drug held or discontinued if, in the opinion of the attending neonatologist, there is no plausible alternative explanation for these findings (such as new thrombus). Not enrolling very preterm infants and excluding infants receiving indomethacin/ibuprofen should minimize the possibility for spontaneous GI perforation. These short term adverse events as defined here, should be reported within 24 hours of discovery to PI.

Also similar to the NRN hydrocortisone extubation trial, we will also specifically monitor for signs of adrenal insufficiency for 3 days after study drug is discontinued, including hypotension and oliguria, as well as hyponatremia and hyperkalemia on clinically obtained electrolyte specimens. Signs of adrenal insufficiency within 3 days after study will be reported within 24 hours of discovery. Previous studies of hydrocortisone at various doses have not reported these signs after discontinuation of a tapering course of the drug.

Patients who develop hypotension and oliguria (shock) significant enough in the judgment of the attending neonatologist to require support with volume and/or vasopressors may have a clinically indicated blood sample drawn for cortisol and may be restarted on hydrocortisone or other therapy for shock at the discretion of the clinical attending. Open-label hydrocortisone should be given at a test dose of 1mg/kg, with continuation of the therapy based on clinical response to the first dose. Persistent hypotension despite inotrope therapy and study drug will be treated per the routine of each center as directed by the treating clinician. Open-label hydrocortisone use will be considered a protocol deviation and it will be reported to DSMC if this deviation occurs in more than 20% of those enrolled.

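### The stated 5 mg/kg/day maximum with open-label hydrocortisone is assured only under the protocol schedule, and the sections on rescue do not agree that this schedule applies

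*Combined protocol and SAP*

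**What the plan says.** Three places in the combined protocol and SAP deal with rescue hydrocortisone.

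- **Section 7.c, Study Intervention (open-label paragraph).** Open-label use is discouraged. If the attending thinks it necessary, stated doses of two inotropes are to be encouraged first. On dosing: "We will recommend dosing of hydrocortisone as outlined in this protocol". On the total: "The max total daily dose that any infant would receive if open-label hydrocortisone were used would be 5 mg/kg/day".
- **Section 8, Other Potential issues (Persistent hypotension).** Care is routine, in keeping with the real-world design. The text then points back to section 7.c: "Open-label hydrocortisone is discouraged but if given, the recommended plan is listed in the methods section above".
- **Section 8, DSMC Safety Monitoring, item a.** After text on shock and adrenal insufficiency: "Open-label hydrocortisone should be given at a test dose of 1mg/kg, with continuation of the therapy based on clinical response to the first dose". The next sentence reads: "Persistent hypotension despite inotrope therapy and study drug will be treated per the routine of each center as directed by the treating clinician". Open-label use is classed as a protocol deviation, reportable to the DSMC if it occurs in more than 20% of those enrolled.

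The study-drug schedule is in section 7.c: "Hydrocortisone dosing will be 2.5 mg/kg/day on day 1, 2 mg/kg/day on days 2 and 3, 1 mg/kg/day on days 4 and 5". The last two days are set at 0.5 mg/kg each. Section 7.c also says that caregivers remain blinded.

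**The concern.** A clinician whose patient stays hypotensive on inotropes and study drug finds different answers in different sections. Section 7.c offers a two-inotrope step and the protocol schedule. The monitoring section offers center routine and, on one reading, a test dose followed by an open-ended course. The maximum in section 7.c is worded as a fact about every infant, yet it rests on one of these routes.

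Masking makes this more than an editorial matter. The clinician cannot know whether the infant already receives up to 2.5 mg/kg/day as study drug, so cannot judge the combined dose. Someone reading the 5 mg/kg/day statement, for example on the DSMC, would take it as an assurance about exposure. Hyperglycemia, hypertension and late-onset infection are among the harms that the plan tracks. Sites that follow different sections may also start rescue at different points, which makes open-label exposure in the placebo arm harder to interpret.

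**Working it through.** **Inputs (section 7.c).** Load 1 mg/kg once; 0.5 mg/kg every 6 h for 12 doses; 0.5 mg/kg every 12 h for 4 doses; 0.5 mg/kg once. Stated maximum 5 mg/kg/day.

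**Step 1: reproduce the daily doses.** Doses fall at 0 h (load), every 6 h from 6 to 72 h, every 12 h from 84 to 120 h, and at 144 h. Day 1 is 1 + 3 × 0.5 = 2.5 mg/kg. Days 2 and 3 are 4 × 0.5 = 2. Days 4 and 5 are 2 × 0.5 = 1. Days 6 and 7 are 0.5. The list and the stated daily doses agree.

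**Step 2: reproduce the maximum.** Let S be the study-drug dose and R the open-label dose, both in mg/kg/day. The total in an active-arm infant is S + R. If R is a first day on the protocol schedule and both courses start together, the total is 2.5 + 2.5 = 5.0, the plan's figure. With later open-label starts the largest 24-hour total falls: 4.5 for the calculated starts from 6 to 48 h (at 24 h, 2.0 + 2.5) and 3.5 or less from 72 h (1.0 + 2.5 at 72 h). Under protocol dosing the stated maximum is therefore correct.

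**Step 3: the condition on which it rests.** The total stays within 5 only if R is no more than 5 − S.

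| Study day | 1 | 2–3 | 4–5 | 6–7 |
|---|---|---|---|---|
| S | 2.5 | 2 | 1 | 0.5 |
| 5 − S | 2.5 | 3 | 4 | 4.5 |

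On day 1 there is no margin above the protocol schedule itself. For an infant on placebo, or one who has finished study drug, S = 0 and only R counts.

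**Step 4: which sections secure the condition.**

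| | Step before rescue | Open-label dosing | Maximum |
|---|---|---|---|
| 7.c | Two inotropes, encouraged | Protocol schedule, recommended | 5 mg/kg/day stated |
| 8, Other Potential issues | Routine care | Refers to 7.c | Not repeated |
| 8, DSMC item a | None stated | Test dose, then by response; center routine for hypotension on study drug | None stated |

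No section requires R to stay within 5 − S.

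**Step 5: illustrations, on assumptions the documents do not make.**

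- Test dose takes the place of the protocol load: 2.5 + (1 + 3 × 0.5) = 5.0, so no excess.
- Test dose at the start of study drug, then a full protocol course with its own load 6 h later: 2.5 + 1 + (1 + 0.5 + 0.5) = 5.5. No section prescribes that second load.
- Center routine resembling a Table 1 regimen of 3 or 3.3 mg/kg/day: 5.5 or 5.8 on day 1, 5.0 or 5.3 on days 2–3, and 4.0 or 4.3 on days 4–5.

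**The case against.** The other side has a good deal to say.

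- **A reader might infer that the maximum is false, or that the plan permits more than 5.** The documents do not support that. No section sets or authorises a larger total, and the monitoring section's silence does not cancel the statement in section 7.c.
- **Other Potential issues goes some way to reconcile the texts.** It places routine care beside the methods plan, and the center-routine sentence can be read as repeating the first half, since it does not mention hydrocortisone. This stands in part. The monitoring section carries no cross-reference, though, and gives its own form of open-label dosing.
- **The test dose may not overlap with study drug.** It follows text on the three days after study drug stops and on restarting hydrocortisone, and it equals the protocol load. This is a plausible reading, but the sentence is not limited to that setting.
- **A reader might infer that any excess falls only on the hydrocortisone arm.** On study day 1 that is true for open-label doses above 2.5 and up to 5 mg/kg/day. Above 5, a placebo infant exceeds the figure as well.
- **A reader might add the highest Table 1 regimens** (6 and 10 mg/kg/day) and report day-1 totals of 8.5 and 12.5. Those regimens come from studies in preterm infants, and nothing shows that they are center practice here. The 3 and 3.3 mg/kg/day examples are not known center practice either, and their totals lie within the 5–7 mg/kg/day that section 7.c cites from small studies.
- **Flexibility is deliberate and safeguards exist.** Randomization is stratified by center, the analysis adjusts for center and is by intention to treat, and steroid use is recorded. Differing site practice therefore does not by itself bias the comparison, though rescue can dilute it. The DSMC trigger concerns how often rescue occurs (0.20 × 646 = 129.2, so at least 130 infants at full enrollment), and does not address dose.

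**Conclusion.** The point stands in a limited form. The sections differ on the step before rescue, on its dosing and on whether any maximum applies. The 5 mg/kg/day figure is arithmetically right as 2.5 + 2.5, but it is assured only if rescue follows a schedule that section 7.c recommends and the monitoring section does not require. The exact size of the gap is the absence of margin: more than 2.5 mg/kg/day open-label on study day 1, or more than 3 on days 2–3, takes an active-arm infant past the stated maximum. How often that would happen, and by how much, cannot be derived from the documents, because center routines are not described. The conclusion assumes only that the center-routine sentence covers infants still on study drug, as its wording says, and that it leaves room for open-label hydrocortisone. This is a safety-relevant inconsistency that should be corrected, but it does not undermine the design or the primary analysis, and it falls short of a must-fix.

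**What to change.** Reconcile section 7.c, Other Potential issues and DSMC Safety Monitoring item a into one rescue instruction, stated once and cross-referenced from the other places. It should say whether the step before open-label hydrocortisone and its dosing differ between infants on study drug and those who have finished, and whether the test dose belongs to one setting or both. Then make the 5 mg/kg/day statement agree with it, either by stating the condition under which it holds (rescue on the protocol schedule) or by withdrawing it. The clinical content, including any dose or threshold, is for the sponsor's clinicians. The cost is protocol wording and a site memo, with no extra patients or data.
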